### 3.13 ADVERSE REACTIONS

Symptoms of bladder irritability, related to the inflammatory response induced, are reported in approximately 60% of patients receiving TICE® BCG. The symptoms typically begin 4–6 hours after instillation and last 24–72 hours. The irritative side effects are usually seen following the third instillation, and tend to increase in severity after each administration.

The irritative bladder adverse effects can usually be managed symptomatically with products such as

pyridium, propantheline bromide, oxybutynin chloride and acetaminophen. The mechanism of action of the irritative side effects has not been firmly established, but is most consistent with an immunological mechanism. There is no evidence that dose reduction or antituberculous drug therapy can prevent or lessen the irritative toxicity of TICE® BCG. "Flu-like" symptoms (malaise, fever, and chills) which may accompany the localized, irritative toxicities often reflect hypersensitivity reactions which can be treated symptomatically. Antihistamines have also been used. Adverse reactions to TICE® BCG tend to be progressive in frequency and severity with subsequent instillation. Delay or postponement of subsequent treatment may or may not reduce the severity of a reaction during subsequent instillation. Although uncommon, serious infectious complications of intravesical BCG have been reported. The most serious infectious complication of BCG is disseminated sepsis with associated mortality. In addition, *M. bovis* infections have been reported in lung, liver, bone, bone marrow, kidney, regional lymph nodes, and prostate in patients who have received intravesical BCG. Some male genitourinary tract infections (orchitis/epididymitis) have been resistant to multiple drug antituberculous therapy and required orchiectomy. **If a patient develops persistent fever or experiences an acute febrile illness consistent with BCG infection, BCG treatment should be discontinued and the patient immediately evaluated and treated for systemic infection (see WARNINGS).** The local and systemic adverse reactions reported in a review of 674 patients with

TABLE V: SUMMARY OF ADVERSE EFFECTS SEEN IN 674 PATIENTS WITH SUPERFICIAL BLADDER CANCER, INCLUDING 153 WITH CARCINOMA *IN SITU*

Adverse Event	Percent of Patients		Adverse Event	Percent of Patients	
	N	Overall (Grade ≥3)		N	Overall (Grade ≥3)
Dysuria	401	60% (11%)	Arthritis/Myalgia	18	3% (<1%)
Urinary Frequency	272	40% (7%)	Headache/Dizziness	16	2% (0)
Flu-Like Syndrome	224	33% (9%)	Urinary Incontinence	16	2% (0)
Hematuria	175	26% (7%)	Anorexia/Weight Loss	15	2% (<1%)
Fever	134	20% (6%)	Urinary Debris	15	2% (<1%)
Malaise/Fatigue	50	7% (0)	Allergy	14	2% (<1%)
Cystitis	40	6% (2%)	Cardiac (Unclassified)	13	2% (1%)
Urgency	39	6% (1%)	Genital Inflammation/		
Nocturia	30	5% (1%)	Abscess	12	2% (<1%)
Cramps/Pain	27	4% (1%)	Respiratory (Unclassified)	11	2% (<1%)
Rigors	22	3% (1%)	Urinary Tract Infection	10	2% (1%)
Nausea/Vomiting	20	3% (<1%)	Abdominal Pain	10	2% (1%)

TABLE VI: MOST COMMON ADVERSE REACTIONS IN SWOG STUDY 8795\*

Adverse Event	Study Arm			
	TICE® BCG (N = 222)		MMC (N = 220)	
	All Grades	Grade ≥3	All Grades	Grade ≥3
Dysuria	115 (52%)	6 (3%)	77 (35%)	5 (2%)
Urgency/Frequency	112 (50%)	5 (2%)	63 (29%)	7 (3%)
Hematuria	85 (38%)	6 (3%)	56 (25%)	5 (2%)
Flu-Like Symptoms	54 (24%)	1 (<1%)	29 (13%)	0
Fever	37 (17%)	1 (<1%)	7 (3%)	0
Pain (Not Specified)	37 (17%)	4 (2%)	22 (10%)	1 (<1%)
Hemorrhagic Cystitis	19 (9%)	3 (1%)	10 (5%)	0
Chills	19 (9%)	0	2 (1%)	0
Bladder Cramps	18 (8%)	0	9 (4%)	0
Nausea	16 (7%)	0	12 (5%)	0
Incontinence	8 (4%)	0	3 (1%)	0
Myalgia/Arthralgia	7 (3%)	0	0	0
Diaphoresis	7 (3%)	0	1 (<1%)	0
Rash	6 (3%)	1 (<1%)	16 (7%)	2 (1%)

**3.14 OVERDOSAGE** Overdosage occurs if more than one vial of TICE® BCG is administered per instillation. If overdosage occurs, the patient should be closely monitored for signs of active local or systemic BCG infection. For acute local or systemic reactions suggesting active infection, an infectious disease specialist experienced in BCG complications should be consulted.

**3.15 DOSAGE AND ADMINISTRATION**

The dose for the intravesical treatment of carcinoma *in situ* and for the prophylaxis of recurrent papillary tumors consists of one vial of TICE® BCG suspended in 50 ml preservative-free saline.

**3.16 Preparation of Agent**

The preparation of the TICE® BCG suspension should be done using aseptic technique. To avoid cross-contamination, parenteral drugs should not be prepared in areas where BCG has been prepared. A separate area for the preparation of the TICE® BCG suspension is recommended. All equipment, supplies and receptacles in contact with TICE® BCG should be handled and disposed of as biohazardous. The pharmacist or individual responsible for mixing the agent should wear gloves and take precautions to avoid contact of BCG with broken skin. If preparation cannot be performed in a biocontainment hood, then a mask and gown should be worn to avoid inhalation of BCG organisms and inadvertent exposure to broken skin.

Option-1 (Using Syringe Method)

Draw 1 ml of sterile, preservative-free saline (0.9% Sodium Chloride Injection U.S.P.) at 4–25°C, into a small syringe (e.g., 3 ml) and add to one vial of TICE® BCG to resuspend. Gently swirl the vial until a homogenous suspension is obtained. Avoid forceful agitation which may cause clumping of the mycobacteria. Dispense the cloudy TICE® BCG suspension into the top end of a catheter-tip syringe which contains 49 ml of saline diluent, bringing the total volume to 50 ml. To mix, gently rotate the syringe.

Option-2 (Using Reconstitution Accessories)

Reconstitution Accessories may be provided with each TICE® BCG product order. Please refer to the Instructions For Use provided with the accessories for a full description of the product reconstitution procedures using these accessories.

The reconstituted TICE® BCG should be kept refrigerated (2–8°C), protected from exposure to direct sunlight, and used within 2 hours. Unused solution should be discarded after 2 hours.

**Note:** DO NOT filter the contents of the TICE® BCG vial. Precautions should be taken to avoid exposing the TICE® BCG to direct sunlight. Bacteriostatic solutions must be avoided. In addition, use only sterile preservative-free saline, 0.9% Sodium Chloride Injection U.S.P. as diluent.

**3.17 HOW SUPPLIED**

TICE® BCG is supplied in a box of one vial of TICE® BCG. Each vial contains 1 to 8 x 10^8 CFU, which is equivalent to approximately 50 mg (wet weight), as lyophilized (freeze-dried) powder. NDC 0052-0602-02.

**3.18 STORAGE**

The intact vials of TICE® BCG should be stored refrigerated, at 2–8°C (36–46°F).

This agent contains live bacteria and should be protected from **direct** sunlight. The product should not be used after the expiration date printed on the label.

**4.0 Staging Criteria**

Bladder cancer  
Primary Tumor (T)

Clinical Stage

- cT1 Invades subepithelial connective tissue (lamina propria)
- cT2 Muscle-invasive
- cT3 Residual mass on exam under anesthesia following TURBT
- cT4 Clinically fixed disease on exam under anesthesia

Pathologic Stage

- pT1 Invades subepithelial connective tissue (lamina propria)
- pT2 Muscle-invasive
- pT3 Invades perivesicle fat
- pT4 Invades adjacent organs (prostate, vagina, uterus, bone, etc...)

Histologic subtypes

Urothelial cell carcinoma (Transitional cell carcinoma)

Squamous cell carcinoma

Adenocarcinoma or glandular carcinoma

Sarcomatoid carcinoma  
Micropapillary carcinoma

Histiologic grade

High-grade      Poorly- or un-differentiated

**5.0      Eligibility Criteria**

**Inclusion Criteria:**

- 5.1      Have suspected or known invasive ( $\geq T1$ ) bladder cancer
- 5.2      Not be in an immunosuppressed state (e.g. HIV +, use of chronic steroids ( $> 1$  month))
- 5.3      Be able to give informed consent
- 5.4      Be age 18 or older

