## 2.0 Background

### 2.1 Overview

Urothelial carcinoma of the bladder (UCB) accounted for 70,530 new cases of cancer and 14,680 cancer-related deaths in the United States during 2010^1. Of these new cases, approximately 25% presented as invasive tumors involving the muscular wall of the bladder. Transurethral resection of bladder tumor (TURBT) is an endoscopic procedure that allows for histopathologic assessment and disease staging. TURBT is the primary diagnostic procedure for new and recurrent bladder tumors. TURBT can also be therapeutic for small or non-muscle invasive tumors. However, when muscle-invasive disease is detected, the standard of care involves bladder removal or radical cystectomy (RC) and urinary diversion.

Despite aggressive surgical treatment with bladder removal, up to 50% of patients undergoing RC will experience disease recurrence. Chemotherapy given both before and after surgery has been investigated to improve survival for these patients. Neoadjuvant chemotherapy renders only a modest improvement in survival- approximately 5-7% absolute benefit in 5-year recurrence free survival. Nevertheless neoadjuvant chemotherapy has not been widely adopted due to concerns of toxicity for a modest benefit. In addition, many consider that giving adjuvant chemotherapy for only those patients with high risk pathologic features is a better alternative than treating all patients with neoadjuvant chemotherapy. Current research efforts, therefore, are aimed towards identifying less toxic regimens for use in the neoadjuvant setting. Such effective therapies, especially using those agents with low to moderate toxicity that are easily administered, would be a significant advance in the treatment of invasive bladder cancer. The development of novel, effective therapies, remains an area of unmet need.

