### 3.7 PRECAUTIONS:

3.7.1 TICE® BCG contains live mycobacteria and should be prepared and handled using aseptic technique (see **Preparation of Agent** subsection of DOSAGE AND ADMINISTRATION). BCG infections have been reported in health care workers preparing BCG for administration. Needle stick injuries should be avoided during the handling and mixing of TICE® BCG. Nosocomial infections have been reported in patients receiving parenteral drugs which were prepared in areas in which BCG was prepared.

3.7.2 BCG is capable of dissemination when administered by intravesical route and serious reactions, including fatal infections, have been reported in patients receiving intravesical BCG. Care should be taken not to traumatize the urinary tract or to introduce contaminants into the urinary system. Seven to 14 days should elapse before TICE® BCG is administered following TUR, biopsy, or traumatic catheterization.

3.7.3 TICE® BCG should be administered with caution to persons in groups at high risk for HIV infection

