**Exclusion Criteria:**

- 5.1.1      Have non-invasive ( $< T1$ ) bladder cancer
- 5.1.2      Is in an immunosuppressed state (e.g. HIV +, use of chronic steroids ( $> 1$  month))
- 5.1.3      Unable to give informed consent
- 5.1.4       $< 18$  or older

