**6.1      Recruitment**

Participants will be recruited through the urology outpatient clinics at the Medical Arts and Research Center (MARC). Attending physicians in the Department of Urology, and selected other personnel who also serve as research staff for this study, will identify prospective study participants. To eliminate selection bias, any patient who presents with invasive bladder cancer and meets the inclusion/exclusion criteria will be given an option to participate in the study. The inclusion of participants or refusal to participate by patients eligible for this study will in no way compromise the quality of health care they will receive.

**Study eligibility** will be determined by investigators and study staff with legitimate access to patient PHI due to their clinical role and/or as members of the research team. Patients who meet the eligibility criteria will be approached by one of the investigators or other members of the study staff to determine whether they are willing to participate in the study. Prior to study entry, the study staff will explain to each potential subject the research objectives, risks and benefits of study participation, alternative treatments available, and the subjects' rights and responsibilities. If the patient agrees to participate, informed consent will be obtained. Research blood and urine may be obtained- OPTIONAL (details in 6.2). Baseline symptoms questionnaires will be administered.

Patients will be approached in a private consult room located within the GU clinic at the MARC. Usual privacy policy practices will be followed. The study procedures and objectives will be described to them and they will be given a copy of the consent document. Participants will also be given contact information for someone they can call with any questions that may arise.

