**6.2.1 Research blood and urine collection & handling OPTIONAL**

Research blood and urine may be collected after signing informed consent (OPTIONAL). Approximately 50 mL or 3.5 tablespoons of blood will be taken from a peripheral vein or an indwelling catheter if present and functional specifically for research studies. Study staff will then provide a urine specimen cup and self-catch instruction to the participant. The participant will be able to do this in the privacy of the clinic restroom.

If collected, research blood and urine specimens will be transported to our lab in the STRF in approved containers by qualified personnel. Additional blood will be collected as needed for initial eligibility screening. Urine will be processed by centrifugation and the supernatant will be stored separately from the pellet. Both blood and urine samples are de-identified in the lab per HIPAA protocol.

Baseline symptoms questionnaires will also be administered.

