#### 6.3.1 Research Urine Collection and Handling Pre and Post-BCG Instillation (research only)

We will collect a urine sample pre-BCG treatment. We will also collect urine samples post-BCG instillations, specifically the second void, which typically occur 4-6 hours post Intravesical BCG treatment. Participants will be given the following options for collection of urine sample post intravesical BCG treatments:

- a) Participant may remain in the clinic for urine collection  
-OR-
- b) Participant may leave the clinic with a urine sample collection cup and biohazard bag. Participant will be given specific instruction to collect second void post intravesical BCG therapy, and return the sample to the clinic.

Study team member will work with participant on how post BCG therapy urine will be collected and returned to the team. Post-BCG urine collection will take place at weekly during the 3-6 weeks of intravesical BCG treatments. Urine will be processed by centrifugation and the supernatant will be stored separately from the pellet.

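### The baseline blood for the primary endpoint is tied to consent, not to the first instillation, so the before/after comparison can span a diagnostic TURBT in some patients

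*Combined protocol and SAP*

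**What the plan says.** - **Entry.** Section 5.0, criterion 5.1: "Have suspected or known invasive" (T1 or higher) bladder cancer. Criterion 5.1.1 excludes patients who "Have non-invasive" disease. Neither says when or how stage must be confirmed relative to consent.
- **Baseline blood.** Section 6.2.1: research blood and urine "may be collected after signing informed consent". In the Section 7.0 calendar, blood appears at Visit 1 (optional), at cystectomy and after cystectomy, and in no BCG week.
- **Gap to treatment.** Section 6.3 allows the first instillation on the day of Visit 1. No maximum gap is given.
- **TURBT.** Section 2.1: "TURBT is the primary diagnostic procedure for new and recurrent bladder tumors". It is not on the calendar, and nothing requires it to precede consent or the baseline draw.
- **Interval from TURBT to BCG.** Section 3.7.2: "Seven to 14 days should elapse before TICE® BCG is administered following TUR, biopsy, or traumatic catheterization". Section 3.5.1 asks for a week or more.
- **Urine.** Section 6.3.1: "We will collect a urine sample pre-BCG treatment". The calendar places this in the BCG weeks, so a pre-instillation sampling point already exists there, for urine only.
- **Endpoint.** Section 8.1 compares blood cells taken before and after BCG in the same patient, without naming the visits. Section 6.0 describes a single-arm design.

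**The concern.** The primary objective credits BCG with any rise in tumor-specific T-cell response. With no control arm, the within-patient difference is the only basis for that attribution, so whatever else happens between the two draws is part of what is measured.

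A patient already resected at Visit 1 contributes a contrast that starts after TURBT. A patient bled at Visit 1 and resected afterwards contributes one that contains TURBT, the waiting period and BCG. The plan permits both and pools them. TURBT removes and disrupts tumor, so it is a plausible competing cause of a changed response to tumor antigen, and the 10% null in Section 9.1 makes no stated allowance for it. A missed post-TURBT, pre-BCG sample cannot be recovered later.

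This is separate from the draw being optional: a mandatory Visit 1 draw would have the same timing problem.

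**Working it through.** **1. The plan's own figure (Section 9.1).** Inputs: null p0 = 0.10, alternative p1 = 0.50, one-sided alpha 5%, power 90%, stated n = 10 evaluable from 25 consented (10/25 = 40%).

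n = [(z_alpha·√(p0(1−p0)) + z_power·√(p1(1−p1))) / (p1−p0)]²

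- One-sided: [(1.645×0.3 + 1.282×0.5)/0.4]² = 8.04, rounded up to 9.
- Two-sided: [(1.960×0.3 + 1.282×0.5)/0.4]² = 9.44, rounded up to 10.
- One-sided with continuity correction: 10.39, rounded up to 11.

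The stated 10 is reproduced to within one patient.

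**2. Decision rule.** The protocol states none. At n = 10, the smallest responder count with exact one-sided error at or below 5% is 4: P(X ≥ 4 | 0.10) = 0.0128, power 0.828. A cut-off of 3 gives 0.0702 and 0.945. I use 4 below.

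**3. Can TURBT fall inside the window?** Suppose TURBT soon after Visit 1, then 7 to 14 days (3.7.2), then 14 days from the first to the third weekly instillation. That is 7+14 = 21 to 14+14 = 28 days. Section 6.3 gives the usual time from enrollment to cystectomy as 4 to 6 weeks (28 to 42 days), so the sequence fits. Such a patient could not have baseline blood and the first instillation on the same day.

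**4. Illustration of size.** Assumptions, none from the documents: BCG has no effect; k of 10 evaluable patients have TURBT between baseline and BCG and meet the response definition with probability q; the other 10−k do so with probability 0.10.

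P(false positive) = P(A + B ≥ 4), with A ~ Bin(k, q) and B ~ Bin(10−k, 0.10).

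For k = 3, q = 0.30, the probabilities of A = 0, 1, 2, 3 are 0.343, 0.441, 0.189, 0.027. The matching B tails (at least 4, 3, 2, 1 of 7) are 0.0027, 0.0257, 0.1497, 0.5217. The sum of products is 0.0009 + 0.0113 + 0.0283 + 0.0141 = 0.0546.

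| k of 10 | q = 0.20 | q = 0.30 | q = 0.40 |
|---|---|---|---|
| 0 | 1.3% | 1.3% | 1.3% |
| 2 | 2.3% | 3.5% | 5.0% |
| 3 | 3.0% | 5.5% | 8.8% |
| 5 | 4.8% | 11.3% | 21.2% |

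Averaging the rates first slightly overstates the risk: five at 30% and five at 10% average 20%, and P(X ≥ 4 | 0.20) = 12.1%, against 11.3% when the two groups are kept apart. With a cut-off of 3, the error is 7.0% at k = 0, and 20.0% and 32.0% at q = 0.30 with k = 3 and k = 5.

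**5. Sample size.** Moving the draw changes no input to Section 9.1, so n = 10 stands.

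**The case against.** A reader might infer that every patient with suspected disease is bled before TURBT, so that no change in such patients can be attributed to BCG. The documents do not support that.

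- No section places TURBT after Visit 1. Suspected disease can also mean that TURBT is done and the stage is pending.
- Section 6.1 says "any patient who presents with invasive bladder cancer and meets the inclusion/exclusion criteria will be given an option to participate". Section 6.3 speaks of fixing the surgery date first, which suggests that many patients are already diagnosed and being scheduled.
- Where Visit 1 and the first instillation share a day, the interval in 3.7.2 leaves no room for a TURBT between them.
- Section 2.1 calls TURBT therapeutic only for small or non-muscle-invasive tumors. T1 patients are eligible, so this limits the point without removing it. No section says that TURBT alters T-cell response; that is a hypothesis.
- Several rows of the table stay at or below 5%. Material inflation needs both a fair number of affected patients and a sizeable TURBT effect.
- A baseline drawn 7 to 14 days after TURBT may still carry an evolving resection effect, and elapsed time is uncontrolled wherever the draw falls.
- Section 6.3.2 lets patients receive BCG from an outside physician, so a draw tied strictly to BCG Week 1 could lose pairs.

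All of this stands as a limit on how often the problem occurs, how large it is, and what the remedy can deliver. None of it is a safeguard written into the plan.

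**Conclusion.** The point holds in its permissive form: the before/after comparison can span a diagnostic TURBT, and the plan does not prevent it. For any such patient, this design cannot tell a resection effect from a BCG effect. How many patients this concerns is unknown.

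The size rests wholly on the assumptions in step 4. At a 30% background rate in affected patients and a cut-off of 4 of 10, the false-positive risk rises from 1.3% to 3.5%, 5.5% or 11.3% with 2, 3 or 5 affected. These figures show sensitivity; they do not estimate bias in this trial. The case for changing the plan is that the protection is specific, cheap and only available prospectively.

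**What to change.** In Sections 6.2.1 and 6.3 and the calendar:

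1. Define the primary-endpoint baseline as blood drawn after the last TURBT or biopsy and before the first instillation, by default at BCG Week 1 with the pre-BCG urine.
2. Accept a Visit 1 draw, or another pre-BCG draw at the study clinic for patients treated by an outside physician, only if no TURBT or biopsy falls between it and the first instillation.
3. Record the TURBT date and report days from TURBT to baseline with the primary result.
4. Repeat the primary analysis without any patient whose TURBT fell between baseline and BCG.
5. State residual TURBT and time effects as a limitation of the single-arm design.

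This moves a blood draw only and leaves treatment timing alone. The number and volume of draws are unchanged under the default. The cost is a wording and calendar amendment, slightly more scheduling effort, and possibly a few lost pairs among patients treated elsewhere. Patients who consent but never start BCG would give no baseline sample, but they cannot contribute to the primary endpoint anyway.

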**Exclusion Criteria:**

- 5.1.1      Have non-invasive ( $< T1$ ) bladder cancer
- 5.1.2      Is in an immunosuppressed state (e.g. HIV +, use of chronic steroids ( $> 1$  month))
- 5.1.3      Unable to give informed consent
- 5.1.4       $< 18$  or older

**6.0      Study Plan**

**6.0      Study Design**

This is a one-arm, open label, interventional study. For the purposes of enrollment "study procedure" refers to intravesical BCG instillation. See below for a description of study procedure.

**6.1      Recruitment**

Participants will be recruited through the urology outpatient clinics at the Medical Arts and Research Center (MARC). Attending physicians in the Department of Urology, and selected other personnel who also serve as research staff for this study, will identify prospective study participants. To eliminate selection bias, any patient who presents with invasive bladder cancer and meets the inclusion/exclusion criteria will be given an option to participate in the study. The inclusion of participants or refusal to participate by patients eligible for this study will in no way compromise the quality of health care they will receive.

**Study eligibility** will be determined by investigators and study staff with legitimate access to patient PHI due to their clinical role and/or as members of the research team. Patients who meet the eligibility criteria will be approached by one of the investigators or other members of the study staff to determine whether they are willing to participate in the study. Prior to study entry, the study staff will explain to each potential subject the research objectives, risks and benefits of study participation, alternative treatments available, and the subjects' rights and responsibilities. If the patient agrees to participate, informed consent will be obtained. Research blood and urine may be obtained- OPTIONAL (details in 6.2). Baseline symptoms questionnaires will be administered.

Patients will be approached in a private consult room located within the GU clinic at the MARC. Usual privacy policy practices will be followed. The study procedures and objectives will be described to them and they will be given a copy of the consent document. Participants will also be given contact information for someone they can call with any questions that may arise.

